6.2.6 Emergency procedures

Such procedures will not be required because no invasive measures will be taken during the study. Patients provide only spontaneously collected urine which means, that no invasive procedure will be used to collect patient's urine such as a catheterization of the urinary bladder.

6.2.7 Blinding

All urine samples will be labelled with a QR code that contains a 9-digit unique number (will not contain any patient identifying information), provided on a laboratory order sheet from Laboratory Limbach, Heidelberg (annex 1) and will be frozen at -20°C immediately at

Confidentiality Statement

This document is confidential and proprietary to Sponsor and HLZ Medizinische Statistik and for restricted circulation and access only. No part of it may be transmitted, reproduced, published or used by any person/s without prior written authorization.

the study center. The codes are attached to the urine tubes before freezing and to the CRF on the prespecified position. Before analysis or upon earlier request by the study center, samples will be collected by Laboratory Limbach and transported within the same day at -20°C to Laboratory Limbach, [name]. Personal performing the LC-MS/MS and evaluating the data are unaware of the patient's treatment.

6.3 Study Time points

During a routine visit in the outpatient care unit of the site, patients who match the entry criteria (based on their medical records at the site) will be informed about the Post Marketing Study, and informed consent will be obtained.

Upon patient's written informed consent the investigator will document the patient's demographic characteristics and record the time of last intake of DOAC in the CRF. Then, the patients will provide a sample of urine and give it to the respective site personnel. The patient requires no further action.

The site personnel will put two aliquots of urine (5 mL) into provided test tubes for analysis of the concentration of DOACs and prepare the sample for shipment according to the shipment instructions.

Then, the site personnel will perform the visual and reflectance photometric reading of the DOAC Dipstick.

Thereafter, the site personnel will complete the questionnaire.

Confidentiality Statement

This document is confidential and proprietary to Sponsor and HLZ Medizinische Statistik and for restricted circulation and access only. No part of it may be transmitted, reproduced, published or used by any person/s without prior written authorization.

Assessment	Day 1
Informed consent	X
Demographic data, medical history	X
Medication history (DOACs, other)	X
Collection of urine sample	X
Visual reading presence/absence of DOACs (IVD)	X
Reflectance photometric reading (DOASENSE Reader) of DOAC Dipstick	X
Urine aliquot for bioanalysis (LC_MS/MS)	X
Completion of questionnaire	X

DOACs: direct oral anticoagulants, IVD: *in vitro* diagnostic test

7. STUDY POPULATION

Patients will be included into the trial if they are on anticoagulant therapy for one week or longer for the indications: non-valvular atrial fibrillation (NVAF) for prevention of cerebral and non-cerebral embolic events and venous thromboembolism (VTE) for prevention of thrombotic events. The inclusion and exclusion criteria define the study population more specifically.

7.1 Inclusion Criteria

Remark: The first inclusion criterion of the Study Plan Version 7.0 eliminated and included into the exclusion criteria due to an overlap of the content.

- Fully signed and dated written informed consent
- Age >18 years
- Patient is either under therapy with Rivaroxaban, Apixaban, and Edoxaban or Dabigatran for at least 1 week

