6.2. Determination of Sample Size

Two groups of medications (Thrombin inhibitor, Factor Xa inhibitors) will be tested with the IVD and test results compared to LC-MS/MS results in urine.

The objective of the investigation is to show that the proportion of false negative and false positive tests with the IVD is below 5%.

Confidentiality Statement

This document is confidential and proprietary to Sponsor and HLZ Medizinische Statistik and for restricted circulation and access only. No part of it may be transmitted, reproduced, published or used by any person/s without prior written authorization.

To improve the strength of the study result, the following adjustments were made in the version 3.0 of the SAP compared to the version 2.0: $\alpha=0.01$ and a 2-sided test with a null proportion of 0.01.

The re-calculation of the required sample size remained unchanged compared to version 2.0 of the document to show that the assumed rate of 2.5% false-negative/false-positive tests is statistically significantly lower than 5% would require 440 patients per each test group including an assumed drop-out rate of 12%, with $\alpha=0.01$ and $\beta=0.20$ (80% power).

This sample size has been assessed with the SAS procedure PROC POWER (SAS Institute Inc., Cary, NC, USA, release 9.3) using the ONESAMPLEFREQ statement under the assumption that the test will be conducted as a 2-sided test with a null proportion of 0.01.

Remark to the calculation of the anticipated dropout rate: **As the present post marketing study is a non-invasive investigation, the dropout rate may be lower than expected.** Only patients fulfilling all of the inclusion criteria and none of the exclusion criteria will be included. Patient's written informed consent is part of the inclusion criteria.

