Legend left figure: Thrombin inhibitor pad, Factor Xa inhibitor and Creatinine pad are depicted with 3 colours: the left colour is described always first, the middle colour always second and the right colour always third in sequence in the text.

Legend right table: Scheme for documentation of colour identified by the observers at centres by comparing the results of the colour of DOAC Dipstick 10 min after incubation with patient's urine with the colours printed on the label of the tube (left, figure) containing the Dipsticks

Confidentiality Statement

This document is confidential and proprietary to Sponsor and HLZ Medizinische Statistik and for restricted circulation and access only. No part of it may be transmitted, reproduced, published or used by any person/s without prior written authorization.

Test Pad 2: (Urine color)

- The color of the pad is white as the respective color marked “norm” on the tube label - the results of pad 1, 3 and 4 are valid.
- The color of the pad is darker than the color printed on the tube label - colors of pad 1, pad 3 and pad 4 may be distorted. The test is invalid.

Test Pad 3 (Medication Apixaban, Edoxaban, Rivaroxaban):

- The color of pad 3 clearly is yellow as the respective color marked “neg.” on the tube label - direct oral Factor Xa inhibitor is absent in the urine sample.
- The color of pad 3 is less yellow than the color marked “neg.” on the tube label, thus the results is “pos.” - direct oral Factor Xa inhibitor is present in urine.
- The color of pad 3 is white as the respective color marked “pos.” on the tube label - direct oral Factor Xa inhibitor is present in urine.

Test Pad 4 (Medication Dabigatran):

- The color of pad 4 is ochre as the respective color marked “neg.” on the tube label - direct oral Thrombin inhibitor is absent in the urine sample.
- The color of pad 4 is between the ochre color marked “neg.” and the rose color marked “pos.” on the tube label - direct oral Thrombin inhibitor is present in urine.
- The color of pad 4 is rose as the respective rose color marked “pos.” on the tube label - direct oral Thrombin inhibitor is present in urine.

If pad 3 and pad 4 are both “pos.”, the test is invalid,
because it is unlikely that a person is treated with both types of DOACs.

Confidentiality Statement

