8.8 Clinical Efficacy and Safety Endpoints

This is a non-interventional study to determine the accuracy of the IVD DOAC Dipstick in comparison to the concentration of the analytes in spontaneously obtained urine sample of patients on chromic treatment with DOACs. Clinical endpoints are not part of the determination of the accuracy of DOAC Dipstick in the study.

The patients will not have additional risks due to participation in the investigation, and will not benefit directly by participating. Only patients who already take oral direct Factor Xa or Thrombin inhibitors will be included into the trial. They will provide a spontaneous urine sample for testing and will not come into contact with the test itself.

Therefore, clinical efficacy and safety endpoints are not defined for this study.

Confidentiality Statement

This document is confidential and proprietary to Sponsor and HLZ Medizinische Statistik and for restricted circulation and access only. No part of it may be transmitted, reproduced, published or used by any person/s without prior written authorization.

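### Every participant takes a DOAC by design, so the 5% false-positive objective is a rate in patients on the other drug class and does not extend to DOAC-free patients

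*SAP*

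**What the plan says.** - **Who enters.** Section 7.1 requires: "Patient is either under therapy with Rivaroxaban, Apixaban, and Edoxaban or Dabigatran for at least 1 week". Section 8.8 repeats it: "Only patients who already take oral direct Factor Xa or Thrombin inhibitors will be included into the trial". Both planned groups, 440 patients each, are treated.
- **Objective.** The section on determination of sample size (6.2) sets out to "show that the proportion of false negative and false positive tests with the IVD is below 5" per cent. That sentence names no population.
- **Primary variable.** Sections 9.1 and 10.2.1 do name the setting as urine from DOAC-treated patients. Section 10.2.1 makes the true-negative rate the primary quantity.
- **Source of negatives.** Section 6.2.1 makes group A the factor Xa inhibitor group. Under 10.2.2 IV, the factor Xa pad uses group B, and dabigatran is analysed in groups B and A.
- **Reference.** Under 8.4 a result is negative or positive by LC-MS/MS concentration, not by the drug prescribed.
- **Both pads positive.** Section 8.2 calls such a strip invalid, "because it is unlikely that a person is treated with both types of DOACs".
- **DOAC-free material.** Row 11 of the table in 10.1.5 lists, as an example for descriptive reporting, non-compliance with both LC-MS/MS and dipstick negative. Section 8.6 adds a negative control urine.

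**The concern.** Section 6.2.5 gives the device's intended use as telling whether DOACs are in the urine or not. Sections 5 and 17 name surgery, bleeding and emergency medicine as settings. There, a false positive means a strip that signals a DOAC in someone who has none. The planned data answer a different question: how often the factor Xa pad turns positive in a dabigatran patient, and the reverse. An unqualified statement that false positives are below 5% would invite readers to carry the cross-class figure over to DOAC-free patients, for whom the plan has no designed denominator.

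The both-positive rule could also weaken the cross-class figure itself. In an adherent patient, a false positive on the other-class pad usually sits beside a true positive, which makes the strip invalid.

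**Working it through.** **1. Numbers available.** The plan gives 440 per group including 12% drop-out: 440 × 0.88 = 387 evaluable, 774 in two groups. DOAC-free patients by design: 0 of 2 × 440 = 880.

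The 440 does not follow from the stated inputs (2.5% against 5%, two-sided alpha 0.01, power 80%). The usual one-sample formula gives ((2.576·√(0.05·0.95) + 0.842·√(0.025·0.975)) / 0.025)² = 768 evaluable, and 768/0.88 = 873. That is a separate matter. Here 440 serves only as the number to be recruited.

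**2. Which urines supply the negatives.**

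| Pad | Planned reference-negatives | Other possible negatives |
|---|---|---|
| Factor Xa | Dabigatran patients | Non-adherent patients at or below the LC-MS/MS cut-off |
| Thrombin | Factor Xa inhibitor patients | The same |

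**3. What incidental DOAC-free urines could show.** The SAP gives no non-adherence figure, so 1% to 3% is an assumption: 774 × 0.01 ≈ 8 and 774 × 0.03 ≈ 23. With zero false positives in n urines, the exact two-sided upper limit is 1 − (a/2)^(1/n). I show a = 0.01 (the test level in 10.1.5) and a = 0.05 (the interval level in 10.2.1).

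| n | 99% upper limit | 95% upper limit |
|---|---|---|
| 8 | 1 − 0.005^(1/8) = 48% | 1 − 0.025^(1/8) = 37% |
| 23 | 1 − 0.005^(1/23) = 21% | 1 − 0.025^(1/23) = 15% |
| 40 | 12.4% | 8.8% |

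For an upper limit below 5% with no false positive at all, 104 DOAC-free urines are needed at 99% and 72 at 95%. These would be 104/774 = 13.4% and 72/774 = 9.3% of evaluable patients.

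**4. Effect of the both-positive rule if invalid strips are excluded.** Assumptions: full adherence, own-pad false negatives 2.5%, independent pads. With true cross-class false-positive rate f, a share 0.975·f of strips is both-positive and leaves. The counted rate is 0.025·f / (1 − 0.975·f).

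| True f | Counted rate |
|---|---|
| 2.5% | 0.06% |
| 5% | 0.13% |
| 10% | 0.0025/0.9025 = 0.28% |
| 20% | 0.005/0.805 = 0.62% |

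In a group of 387 with f = 10%, about 38.7 strips would carry a cross-class false positive. About 37.7 would drop out and about 1 would be counted.

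**The case against.** The strongest reply is that the scope is already declared. The introduction and sections 9.1 and 10.2.1 name DOAC-treated patients. In the sample-size section, the sentence just before the objective reads "Two groups of medications (Thrombin inhibitor, Factor Xa inhibitors) will be tested with the IVD". Section 10.2.2 IV discloses which group feeds which pad. No sentence claims a false-positive rate in untreated people, and enrolling treated patients only is a legitimate design. All this stands. What remains is that the sentence carrying the 5% limit is unrestricted while the primary variable is restricted, so the two should be aligned.

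Four stronger readings are tempting but not supported:

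- *That the negatives come only from the other class.* The reference is LC-MS/MS, so a non-adherent patient also counts as negative.
- *That readers face a forced choice between pads.* Enrolment tells them that some DOAC is expected. In 6.3, however, the investigator records the last intake and site personnel read the strip, and the SAP does not say whether the reader knows the class. A double-negative result is foreseen in row 11.
- *That invalid strips will be dropped.* The SAP is silent, and row 11 lists both-positive results for descriptive reporting. The figures in step 4 are therefore conditional.
- *That the negative control urine settles the matter either way.* Its number of runs is not fixed: section 8 has controls before and after every 12th patient, 8.6 at the start and after every 12th. Even 104 runs without a false positive would be repeat readings of one manufactured material, not urines from 104 patients.

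**Conclusion.** The concern holds as a mismatch between claim and design. By design each pad's false-positive rate is estimated almost entirely in patients on the other class, so the 5% objective should not be read as covering DOAC-free patients. Incidental cases cannot fill the gap: under the assumed 1% to 3%, the 99% upper limit stays between 48% and 21% even with no false positive. Row 11's only example of such cases is one in which the dipstick is negative too, so no planned table would clearly show a positive pad in a DOAC-free patient. The unsettled handling of both-positive strips also matters: if they are excluded, a true cross-class rate well above 5% could be reported as well below 1%, given the independence and adherence assumptions of step 4.

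A reader might infer that the plan asserts specificity in untreated patients, or that the study is unsound without an untreated group. The document supports neither.

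**What to change.** 1. In the sample-size section (6.2) and in 10.2.1, define the 5% claim as the false-positive rate of the factor Xa pad in patients treated with a thrombin inhibitor, and of the thrombin pad in patients treated with a factor Xa inhibitor. State that specificity for urine without any DOAC is not a study claim.
2. Add one table of pads 3 and 4 in participants who are LC-MS/MS-negative for all four drugs, with exact intervals and no 5% claim.
3. For the accuracy analysis, count a positive pad that is LC-MS/MS-negative for its class as a false positive even when the strip is labelled invalid, or report the rate with and without such strips. This concerns counting only and leaves the instructions for use untouched.
4. Report the control-urine readings as already planned (10.2.2 XV; tables 22 and 23 in sections 18 and 19), without a binomial claim about patients.

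The cost is some wording and one small table from data already collected, with no extra patients. The downside is a narrower and possibly less favourable claim. The alternative, a DOAC-free group sized on the SAP's own inputs, would take 873 further patients (step 1), and the narrower claim does not need it.

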7.2 Exclusion criteria

- Patient not able to provide urine samples.

Confidentiality Statement

This document is confidential and proprietary to Sponsor and HLZ Medizinische Statistik and for restricted circulation and access only. No part of it may be transmitted, reproduced, published or used by any person/s without prior written authorization.

- Patient not able to understand the informed consent or severely mentally disabled.
- Patients in the end-stage of a severe disease.

Patients are free to withdraw their participation any time following written informed consent.

The data of these patients will be discarded and eliminated from the assessment (drop-out patients).

7.3 Population characteristics

The following data will be recorded for each patient in a CRF:

- Age (years)
- Gender (male, female)
- Body weight (kg)
- Body height (cm)
- Medical and surgical history relevant to DOAC treatment
- Medication history – DOAC (type, dose, start of treatment, last intake before providing urine sample)
- Other medication history relevant to DOAC therapy
- Data will be taken from the patient's medical records.

8. DEFINITIONS AND DERIVED VARIABLES

All measurements are carried out according to standard medical methods of the investigational site. The personnel involved are adequately trained in required measurements.

Patients will collect a sample of urine into the container provided by DOASENSE GmbH and hand it over to the site personnel.

The site personnel will first perform

- 1) Visual testing using DOAC Dipstick according to the instructions for use (annex 2)

Confidentiality Statement

This document is confidential and proprietary to Sponsor and HLZ Medizinische Statistik and for restricted circulation and access only. No part of it may be transmitted, reproduced, published or used by any person/s without prior written authorization.

Sponsor Name: DOASENSE GmbH
Statistical Analysis Plan (SAP)
Version No.: 3 Date: 2019-05-15

Sponsor Study No.: DOA-CS-002
ClinicalTrials.gov ID: NCT03182829
HLZ Medizinische Statistik Study No.: 1-2019

- 2) immediately thereafter analyze the patient's DOAC Dipstick with the DOASENSE Reader (annex 3). The printout of the DOASENSE Reader is attached to the respective field in the CRF with the numbers to be written with a pencil beside the printout because the thermopaper of the printout may lose colour over time.
- 3) put two aliquots of 5 mL urine into the tubes provided for measurements of DOACs and creatinine.
- 4) to discard the remaining urine.
- 5) Analysis of DOASENSE Control Urines that comprise a negative and positive control for DOACs and creatinine before and after inclusion of every 12th patient
- 6) Compilation of a questionnaire on the handling of DOAC Dipstick and its analysis by the study personnel that perform the test (visual and with DOASENSE Reader) after having performed the analyses of the 5th and 15th patient

All sites will receive the same model/type of reflectance photometric dipstick color reader (DOASENSE Reader).

8.1 Demographic variables

The variables are described in paragraph 2.3. Medical personnel at the site will record the patient's demographic data in a prepared Case Report Form (annex 4).

The urine samples will be tested in the outpatient care unit with the IVD and the DOASENSE Reader. In addition, aliquots of urine will be analyzed by LC-MS/MS.

8.2 Visual assessment of colours of pads of DOAC Dipstick

Note: Site personnel with known red-green blindness/ weakness cannot perform the test.

The site personnel will perform the visual urine test as follows:

The test strip is dipped into urine or into control samples for 2 to 3 seconds, so all test pads are wet with urine. Then, the test strip is placed on a flat surface (room temperature, at light) with

Confidentiality Statement

This document is confidential and proprietary to Sponsor and HLZ Medizinische Statistik and for restricted circulation and access only. No part of it may be transmitted, reproduced, published or used by any person/s without prior written authorization.

the pads facing upwards (so color changes can be seen). After 10 Minutes the site personnel will compare the results visually with the reference scale on the dipstick container. Then, the dipstick will be placed into the reflectance photometric reader according to the handling instructions.

The study personnel will document the results in the CRF and the printout of the reflectance photometric color reader (DOASENSE Reader) will be copied and fixed with an adhesive into the CRF.

After 10 minutes, the reactions on the pads are completed. The colours of the pads are identified by naked eye of the study personnel and judged as follows by comparing the colour label attached to the test tube.

The text for the identification of the colour by the observer is taken form the instructions for use (annex 2) and as follows:

[figure not shown]
Test Pad 1: (Creatinine)

- The color of pad 1 corresponds to colors “norm.” on the tube label - creatinine in urine is normal. Pad 3 and pad 4 can be evaluated.
- The color of pad 1 is darker than the colors “norm.” on the tube label - high creatinine does not affect DOAC excretion into urine. Pad 3 and pad 4 can be evaluated.
- The color of pad 1 is “low” or lighter than the respective color of the tube label - creatinine in urine is low, indicating renal insufficiency.

Colors of pad 3 and pad 4 may be false negative.

Confidentiality Statement

This document is confidential and proprietary to Sponsor and HLZ Medizinische Statistik and for restricted circulation and access only. No part of it may be transmitted, reproduced, published or used by any person/s without prior written authorization.

Legend left figure: Thrombin inhibitor pad, Factor Xa inhibitor and Creatinine pad are depicted with 3 colours: the left colour is described always first, the middle colour always second and the right colour always third in sequence in the text.

Legend right table: Scheme for documentation of colour identified by the observers at centres by comparing the results of the colour of DOAC Dipstick 10 min after incubation with patient's urine with the colours printed on the label of the tube (left, figure) containing the Dipsticks

Confidentiality Statement

This document is confidential and proprietary to Sponsor and HLZ Medizinische Statistik and for restricted circulation and access only. No part of it may be transmitted, reproduced, published or used by any person/s without prior written authorization.

Test Pad 2: (Urine color)

- The color of the pad is white as the respective color marked “norm” on the tube label - the results of pad 1, 3 and 4 are valid.
- The color of the pad is darker than the color printed on the tube label - colors of pad 1, pad 3 and pad 4 may be distorted. The test is invalid.

Test Pad 3 (Medication Apixaban, Edoxaban, Rivaroxaban):

- The color of pad 3 clearly is yellow as the respective color marked “neg.” on the tube label - direct oral Factor Xa inhibitor is absent in the urine sample.
- The color of pad 3 is less yellow than the color marked “neg.” on the tube label, thus the results is “pos.” - direct oral Factor Xa inhibitor is present in urine.
- The color of pad 3 is white as the respective color marked “pos.” on the tube label - direct oral Factor Xa inhibitor is present in urine.

Test Pad 4 (Medication Dabigatran):

- The color of pad 4 is ochre as the respective color marked “neg.” on the tube label - direct oral Thrombin inhibitor is absent in the urine sample.
- The color of pad 4 is between the ochre color marked “neg.” and the rose color marked “pos.” on the tube label - direct oral Thrombin inhibitor is present in urine.
- The color of pad 4 is rose as the respective rose color marked “pos.” on the tube label - direct oral Thrombin inhibitor is present in urine.

If pad 3 and pad 4 are both “pos.”, the test is invalid,
because it is unlikely that a person is treated with both types of DOACs.

Confidentiality Statement

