8.5 Analysis of Creatinine in urine

Creatinine is determined in urine by the method of Jaffe et al at Laboratory Limbach (24). Normal values are below 0.25 g/l. Values below 0.25 g/l are interpreted as "low" and higher values are interpreted as "normal". The normal range of creatinine may change upon the results of the measurement because reduced renal function with low creatinine is a contraindication for the therapy with a DOAC. If a diagnosis of renal insufficiency is documented in a patient, low creatinine value has to be interpreted as correct low. However, changes may be required upon the results of the determination of creatinine by laboratory Limbach. These decisions are made by the Steering Committee.

Data are transferred unchanged by software to an Excel file at Laboratory Limbach. This file is stored on a password secured USB flash drive and brought to the Institute for Biometry and Statistics by the Co-ordinating Investigator. [name] imports the data from Excel to SAS. Treatment of patients and data of LC-MS/MS remain blinded during this procedure. Six months after termination of the analysis of DOACs by LC-MS/MS and creatinine by Jaffe Method urine samples are discarded. This period may be changed upon request of the Sponsor of the study.

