10.1.11 Dropouts and Missing Data

Subject inclusion/exclusion criteria will be determined at baseline visit, and subjects who do not meet all criteria will not be entered into the study. Those subjects with signed informed consent deemed eligible to participate will be allocated a 2-digit number of the center at which patients are recruited followed by a 3-digit number that is consecutive according to the inclusion.

If patients do not fulfil posthoc all inclusion or exclusion criteria – except missing or late signature of written informed consent – e.g. reduced renal function, less than 7 days on therapy, intake of two different DOACs at the same time, change of dose of DOAC within the past 7 days and other findings, they will be evaluated individually and may be described as case reports.

If there is no "informed consent" or if the date of the "informed consent" is after the "start date" it is a dropout.

If a subject withdraws consent at any time after entering the study, will result in patient removal of all data from the study.

If data (dd.mm.yyyy) is specified with 99.99.yyyy in the table, it will be replaced as follows:

1. 99.99.yyyy (day and month missing) is replaced by 01.07.yyyy. Example: 99.99.2017 = 01.07.2017
2. 99.mm.yyyy (day missing) is replaced by 15.mm.yyyy. Example: 99.08.2018 = 15.08.2018

For twice daily intake of medication: If time (hour/min) is not specified, the mean of the time (i.e. 02:00 p.m. or 02:00 a.m., between 08:00 a.m. and 08:00 p.m. or 08:00 a.m. and 08:00 p.m.,

Confidentiality Statement

This document is confidential and proprietary to Sponsor and HLZ Medizinische Statistik and for restricted circulation and access only. No part of it may be transmitted, reproduced, published or used by any person/s without prior written authorization.

whatever applies according the documentation in the CRF, i.e. is taken for the analysis, respectively.

For once daily intake of medication: If time (hour/min) is not specified, the mean of the time (i.e. 08:00 p.m.) between 08:00 a.m. at the day before and the day of urine sampling is taken for analysis.

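### Low creatinine in a spot urine is read as a sign of renal insufficiency, and section 8.5 lets that reading influence the creatinine limit and the scoring of the creatinine pad

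*SAP*

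**What the plan says.** Section 8.2 (Test Pad 1) gives the meaning of a pad that reads low or lighter: "creatinine in urine is low, indicating renal insufficiency". It then warns: "Colors of pad 3 and pad 4 may be false negative". It states that this reading text comes from the instructions for use.

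Section 8.5 applies a bare concentration limit to the laboratory value: "Values below 0.25 g/l are interpreted as" low, and higher values as normal. It adds three things of its own:

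- The normal range may change once the measurements are available. The reason given is that "reduced renal function with low creatinine is a contraindication for the therapy with a DOAC".
- Where a renal diagnosis is documented, a low value is to be taken as a correct low.
- Further changes may follow from the laboratory results, and the Steering Committee decides on them.

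The specimen is a single untimed urine (8.8): "They will provide a spontaneous urine sample for testing". Section 7.3 lists "Medical and surgical history relevant to DOAC treatment" among the recorded data.

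Creatinine is used in items VII and IX, in the creatinine accuracy comparisons (items XI and XII of 10.2.2, numbered XII and XIII in 9.2.2), and in post-text tables 12, 13 and 17. The SAP nowhere names dilute urine as a cause of a low value.

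**The concern.** The concentration of creatinine in a spot urine depends on how much creatinine is put out and in how much water. A low reading can come from a patient with normal kidneys who has been drinking or who has little muscle. A patient with stable renal impairment and ordinary urine volume can read normal.

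Two sets of results are at stake:

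- **Creatinine-pad accuracy.** If a diagnosis can make a low value correct, or if the limit moves because low values look implausible in treated patients, the accuracy figures no longer compare the pad with the measured concentration alone.
- **Explanation of DOAC-pad errors.** Dilution lowers creatinine and drug together. If false-negative DOAC pads cluster in low-creatinine samples, the wording of 8.2 invites a report of a kidney effect. Dilution is at least as available an explanation and can occur in any patient.

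**Working it through.** The SAP gives no figure on this point to reproduce. The check is a mass balance, followed by a reading of the rules in 8.5.

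**Inputs from the SAP:** limit 0.25 g/l (8.5); spontaneous urine (8.8); negative control with 1.5 g/L creatinine and positive control with 800 ng/mL drug (8.6); LC-MS/MS upper limit of normal 4.0 ng/ml (8.4).

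**Assumptions, not in the SAP:** creatinine production G of 0.5 to 2.0 g/day (1.2 in the example), urine volume V of 1 to 5 l/day, filtration rates of 90, 60 and 30 ml/min.

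**1. Does the filtration rate (GFR) enter?** Urine concentration is U = GFR × P / V, where P is plasma creatinine. At steady state GFR × P = G, so U = G / V and the filtration rate cancels for given G and V. With G = 1.2 g/day, P = 1.2 / (GFR × 1.44) g/l:

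| Filtration rate (ml/min) | Plasma creatinine (mg/dl) | U at 1 l/day (g/l) | U at 2 l/day (g/l) | U at 5 l/day (g/l) |
|---|---|---|---|---|
| 90 | 0.93 | 1.20 | 0.60 | 0.24 |
| 60 | 1.39 | 1.20 | 0.60 | 0.24 |
| 30 | 2.78 | 1.20 | 0.60 | 0.24 |

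Plasma creatinine triples down the table while the urine columns do not change. Only volume takes the value below 0.25 g/l.

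**2. Urine flow at which the limit is reached.** V = G / 0.25:

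- G = 0.5 g/day: 2.0 l/day (1.39 ml/min)
- G = 1.0 g/day: 4.0 l/day (2.78 ml/min)
- G = 1.2 g/day: 4.8 l/day (3.33 ml/min)
- G = 2.0 g/day: 8.0 l/day (5.56 ml/min)

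A spot sample reflects the flow before that one void, so the flow need not last all day. Measured from the plan's own normal control, the limit is a dilution of 1.5 / 0.25 = 6-fold.

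**3. What dilution does to the drug.** The same six-fold dilution of a urine holding 800 ng/mL, the control concentration used here only as an illustration, gives 800 / 6 = 133 ng/ml. That is still about 33 times the 4.0 ng/ml limit, so LC-MS/MS stays positive. Whether the strip stays positive depends on its detection threshold, which the SAP does not give. If the strip turns negative, the sample is a false negative with a low pad 1 and no kidney disease.

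**4. The correct-low rule.** The text does not say whether the low value is the pad or the Jaffe result.

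- *If it means the pad:* a low pad with Jaffe at or above 0.25 g/l is a pad error by concentration. With a renal diagnosis on file, the rule makes it correct. The same strip result on the same concentration is scored differently in two patients.
- *If it means the Jaffe value:* the rule confirms the reference reading in diagnosed patients and leaves low values in the others open to question. Those are the values for which 8.5 permits the range to move.

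Either way, correctness depends on a diagnosis as well as on the concentration.

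**5. Moving the limit.** Section 8.5 gives its renal premise as the reason why the range may change after measurement. By steps 1 and 2 a low value in a treated patient needs no renal explanation, so that reason does not support a change.

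**The case against.** The phrase in 8.2 is reproduced label text for a marketed device, and its practical consequence is only the warning about pads 3 and 4. That warning holds whatever the cause of the low reading. Section 8.5 names its categories only low and normal. Items VII and IX enter creatinine, not renal function, and tables 12, 13 and 17 carry no renal label. The 8.5 rule runs from a documented diagnosis to a low value, not the reverse. The physiology can also be put too strongly: cancellation holds at steady state for given output and volume, and kidney disease can impair the ability to concentrate urine.

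Most of this stands, and it rules out several stronger readings that a reader might infer:

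- *That patients will be classed as renal cases from pad 1 or Jaffe.* No section does this. Section 10.1.11 lists "reduced renal function, less than 7 days on therapy" among findings to be evaluated individually, but does not link their detection to urine creatinine.
- *That DOAC-pad errors will be reassigned because pad 1 is low.* No rule says so.
- *That urine creatinine is the only renal information.* Section 7.3 takes medical history from the records, and the protocol and case report form are not shown.
- *That the number affected can be estimated.* Log-normal spot values with geometric mean 0.6 to 1.0 g/l and geometric SD 1.8 to 2.3 would put 0.9% to 14.7% below the limit, or 8 to 130 of 880. Those parameters are assumed. The count is of low readings, not misclassified patients, and 880 (2 × 440) includes the 12% drop-out allowance; without it, 880 × 0.88 is about 774.

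What the objection does not remove is 8.5. The reason for moving the limit and the correct-low rule are additional SAP text on the laboratory value, and both bear on how creatinine results are scored.

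**Conclusion.** The concern holds in a limited form. Low creatinine in one spontaneous urine is non-specific, and treating it as a renal sign is unsound. The consequence lies in secondary results. Accuracy of the creatinine pad (items XI and XII of 10.2.2, tables 12 and 13) could depend on diagnosis or on a limit moved after the data. Associations in items VII and IX and table 17 could be wrongly explained as kidney effects.

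The primary comparison of strip and LC-MS/MS on the same urine does not use creatinine and is unaffected. The size cannot be derived from the SAP, which gives neither the distribution of urine creatinine nor the frequency of documented renal insufficiency. The physiological argument assumes steady state. The output and volume figures are illustrative, but the cancellation of filtration rate does not depend on them.

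**What to change.** - In 8.2, 8.5 and the creatinine analyses, describe pad 1 and Jaffe creatinine only as a urine concentration, low or normal, non-specific as to cause. If the label text is kept in 8.2, add that the analysis does not adopt its renal interpretation.
- Judge the creatinine pad against the measured Jaffe concentration alone, at a limit fixed before the data are seen. Remove the correct-low rule and the renal reason for changing the range. While doing so, reconcile the two consecutive sentences of 8.5 that call values below 0.25 g/l first normal and then low.
- Take renal status only from the medical history already recorded under 7.3.
- In items VII and IX, enter urine creatinine and documented renal insufficiency as separate factors, and report table 17 without a renal label.

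The cost is SAP wording and one factor coded from history already collected; no new procedure is needed. The drawback is that documented renal status may be incomplete for some patients, which the report should state.
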